#### 5.7.3 Use in Pregnancy

If a subject inadvertently becomes pregnant while on treatment with pembrolizumab, the subject will immediately be removed from the study. The site will contact the subject at least monthly and document the subject's status until the pregnancy has been completed or terminated. The outcome of the pregnancy will be reported to the Sponsor and to Merck without delay and within 24 hours to the Sponsor and within 2 working days to Merck if the outcome is a serious adverse experience (e.g., death, abortion, congenital anomaly, or other disabling or life-threatening complication to the mother or newborn).

The study investigator will make every effort to obtain permission to follow the outcome of the pregnancy and report the condition of the fetus or newborn to the Sponsor. If a male subject impregnates his female partner the study personnel at the site must be informed

immediately and the pregnancy reported to the Sponsor and to Merck and followed as described above and in Section 7.2.2.

## 5.7.4 Use in Nursing Women

It is unknown whether pembrolizumab is excreted in human milk. Since many drugs are excreted in human milk, and because of the potential for serious adverse reactions in the nursing infant, subjects who are breast-feeding are not eligible for enrollment.

## 5.8 Subject Withdrawal/Discontinuation Criteria

Subjects may withdraw consent at any time for any reason or be dropped from the trial at the discretion of the investigator should any untoward effect occur. In addition, a subject may be withdrawn by the investigator or the Sponsor if enrollment into the trial is inappropriate, the trial plan is violated, or for administrative and/or other safety reasons. Specific details regarding discontinuation or withdrawal are provided in Section 7.1.4 – Other Procedures.

A subject must be discontinued from the trial for any of the following reasons:

- The subject or legal representative (such as a parent or legal guardian) withdraws consent.
- Confirmed radiographic disease progression

Note: For unconfirmed radiographic disease progression, please see Section 5.2.2

Note: A subject may be granted an exception to continue on treatment with confirmed radiographic progression if clinically stable or clinically improved, please see Section 7.1.2.7.1

- Unacceptable adverse experiences as described in Section 5.2.1.2
- Intercurrent illness that prevents further administration of treatment
- Investigator's decision to withdraw the subject
- Confirmed positive serum pregnancy test
- Noncompliance with trial treatment or procedure requirements
- Subject is lost to follow-up
- Completed 24 months of uninterrupted treatment with pembrolizumab or 35 administrations of study medication, whichever is later.

Note: 24 months of study medication is calculated from the date of first dose. Subjects who stop pembrolizumab after 24 months may be eligible for up to one year of additional study treatment if they progress after stopping study treatment provided they meet the requirements detailed in Section 7.1.7.3.

- Administrative reasons
- A second episode of grade ≥ 2 pneumonitis mandates discontinuation of study therapy.

The End of Treatment and Follow-up visit procedures are listed in Section 6 (Protocol Flow Chart) and Section 7.1.5 (Visit Requirements). After the last dose of study drug, each subject will be followed for 30 days for adverse event monitoring (serious adverse events will be collected for 90 days after the end of treatment as described in Section 7.2.3.1). Subjects who discontinue for reasons other than progressive disease will have post-treatment follow-up for disease status until disease progression, initiating a non-study cancer treatment, withdrawing consent or becoming lost to follow-up. After documented disease progression each subject will be followed by telephone for overall survival until death, withdrawal of consent, or the end of the study, whichever occurs first.

## 5.8.1 Discontinuation of Study Therapy after CR

Discontinuation of treatment may be considered for subjects who have attained a confirmed CR that have been treated for at least 24 weeks with pembrolizumab and had at least two treatments with pembrolizumab beyond the date when the initial CR was declared. Subjects who then experience radiographic disease progression may be eligible for up to one year of additional treatment with pembrolizumab via the Second Course Phase at the discretion of the investigator if no cancer treatment was administered since the last dose of pembrolizumab, the subject meets the safety parameters listed in the Inclusion/Exclusion criteria, and the trial is open. Subjects will resume therapy at the same dose and schedule at the time of initial discontinuation. Additional details are provided in Section 7.1.7.3.

## 5.9 Subject Replacement Strategy

#### 5.10 Clinical Criteria for Early Trial Termination

Early trial termination will be the result of the criteria specified below:

- 1. Quality or quantity of data recording is inaccurate or incomplete
- 2. Poor adherence to protocol and regulatory requirements
- 3. Incidence or severity of adverse drug reaction in this or other studies indicates a potential health hazard to subjects
- 4. Plans to modify or discontinue the development of the study drug

In the event of Merck decision to no longer supply study drug, ample notification will be provided so that appropriate adjustments to subject treatment can be made.

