#### 2.0 TRIAL DESIGN

#### 2.1 Trial Design

We propose a phase I/randomized phase II clinical trial of pembrolizumab and vorinostat in ECOG 0-1 patients with immune therapy naïve and immune therapy pretreated locally advanced or metastatic NSCLC who have progressed through one prior line of therapy (**Figure 1**). The study would begin with a phase I dose escalation utilizing the modified continuous reassessment method (O'Quigley, Pepe, & Fisher, 1990). This would be followed by a phase I expansion at the maximum tolerated dose (MTD) in 18 NSCLC patients who have been previously treated with anti-PD-1 or anti-PD-L1 therapy. In parallel, a separate phase II arm will randomize 78 patients to a pembrolizumab alone group and a pembrolizumab plus vorinostat group.

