#### **5.2 Trial Treatments**

The phase I dose escalation will include a fixed dose of Pembrolizumab 200mg IV every 3 weeks and escalating doses of vorinostat (three dose levels) to determine the MTD to be used in the expansion group and the randomized phase II portion of the trial. Once a MTD is determined, the phase Ib expansion and randomized phase two portions of the trial can begin accrual. Cycle 1, day 1 will start with Pembrolizumab concurrent with continuous daily oral therapy with vorinostat.

Table 6. Vorinostat dose levels in phase I dose escalation phase.

Dose Level	Vorinostat Dose, Route, Frequency	Pembrolizumab Dose, Route, Frequency	Use
-1	100mg PO Daily	200mg IV Q3 weeks	Experimental
1	200mg PO Daily	200mg IV Q3 weeks	Experimental
2	400mg PO Daily	200mg IV Q3 weeks	Experimental

Trial treatment should begin within 3 days of randomization or as close as possible to the date on which treatment is allocated/assigned.

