#### 5.2.1.2 Dose Modification

Adverse events (both non-serious and serious) associated with pembrolizumab exposure may represent an immunologic etiology. These adverse events may occur shortly after the first dose or several months after the last dose of treatment. Pembrolizumab must be withheld for drug-related toxicities and severe or life-threatening AEs as per **Table 7** below. See Section 5.6.1 and Events of Clinical Interest Guidance Document for supportive care guidelines, including use of corticosteroids.

Table 7. Dose Modification Guidelines for Drug-Related Adverse Events

Toxicity	Hold Treatment For Grade	Timing for Restarting Treatment	Discontinue Subject
Diarrhea/Colitis	2-3	Toxicity resolves to Grade 0-1.	Toxicity does not resolve within 12 weeks of last dose or inability to reduce corticosteroid to 10 mg or less of prednisone or equivalent per day within 12 weeks.
	4	Permanently discontinue	Permanently discontinue
AST, ALT, or Increased Bilirubin	2	Toxicity resolves to Grade 0-1	Toxicity does not resolve within 12 weeks of last dose.
	3-4	Permanently discontinue (see exception below) 	Permanently discontinue
Type 1 diabetes mellitus (if new onset) or Hyperglycemia	T1DM or 3-4	Hold pembrolizumab for new onset Type 1 diabetes mellitus or Grade 3- 4 hyperglycemia associated with evidence of beta cell failure.	Resume pembrolizumab when patients are clinically and metabolically stable.
Hypophysitis	2-3	Toxicity resolves to Grade 0-1	Toxicity does not resolve within 12 weeks of last dose or inability to reduce corticosteroid to 10 mg or less of prednisone or equivalent per day within 12 weeks.
	4	Permanently discontinue	Permanently discontinue
Hyperthyroidis m	3	Toxicity resolves to Grade 0-1	Toxicity does not resolve within 12 weeks of last dose or inability to reduce corticosteroid to 10 mg or less of prednisone or equivalent per day within 12 weeks.
	4	Permanently discontinue	Permanently discontinue
Hypothyroidism	2-4	Therapy with pembrolizumab can be continued while treatment for the thyroid disorder is instituted	Therapy with pembrolizumab can be continued while treatment for the thyroid disorder is instituted.
Infusion Reaction	3-4	Permanently discontinue	Permanently discontinue
Pneumonitis	2	Toxicity resolves to Grade 0-1	Toxicity does not resolve within 12 weeks of last dose or inability to reduce corticosteroid to 10 mg or less of prednisone or equivalent per day within 12 weeks.

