In Scenario 3 with 200mg as true MTD, the probability of 200mg as MTD is 53.2% by mCRM design and 34.8% by 3+3 design. There are 58.2% patients assigned to the 200mg by the mCRM design compared to 49.4% by the 3+3 design.

In Scenario 4 with 400mg as true MTD, the probability of 400mg as MTD is 83.5% by the mCRM design and 44.8% by the 3+3 design. Both designs have 42.7%-57.3% patients assigned to the 400mg dose level (mCRM: 57.3%; 3+3 design: 42.7%).

These simulations show that the proposed mCRM design with 12 subjects is superior to the 3+3 design in that it has a higher probability of estimating the MTD correctly.

Table 13. The mCRM would allow more patients to be exposed to the MTD as compared to the 3+3 design. The simulation scenarios are associated with a probability of a dose to be selected as the MTD (Percent Recommendation) and a proportion of patients assigned to each dose level (Percent Experimentation).

		Probability of a dose to be selected as MTD  (Percent Recommendation)  Dose Cohort					Probability of patients assigned to each dose level  (Percent Experimentation)			
							Dose Cohort			
	Method	<100mg	100mg	200mg	400mg		100mg	200mg	400mg	
Scenario 1										
(Toxicity as expected:	CRM			16.3	83.3					
400mg as true MTD)	(n=12)	0.0%	0.4%	%	%		1.6%	41.7%	56.7%	
	3+3		10.1	44.8	44.8					
	(n=9.38)	0.3%	%	%	%		5.5%	51.8%	42.7%	
Scenario 2										
(greater than expected:	CRM		54.5	36.6						
100mg as true MTD)	(n=12)	0.0%	%	%	8.9%		34.3%	53.4%	12.3%	

	3+3 (n=10.16)	55.7 %	20.4 %	21.4 %	2.5%	40.3%	48.5%	11.2%
Scenario 3								
(greater than expected: 200mg as true MTD)	CRM (n=12)	0.0%	21.7 %	53.2 %	25.1 %	18.6%	58.2%	23.3%
	3+3 (n=10.57)	16.5 %	40.2 %	34.8 %	8.5%	30.9%	49.4%	19.7%
Scenario 4								
(greater than expected: 400mg as true MTD)	CRM (n=12)	0.0%	1.0%	15.5 %	83.5 %	1.8%	40.9%	57.3%
	3+3 (n=9.38)	1.5%	8.9%	44.8 %	44.8 %	5.5%	51.8%	42.7%

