#### 8.2.6 Sample size calculation and Interim Analysis.

From historical data(Edward B Garon, 2014) (Socinski, Checkmate 026, EMSO 2016; Hellman et al, Keynote 001, WCLC, 2015; ), we will consider 25% response rate as not warranting further study. We will use 45% response rate as a promising result to pursue further study. In other words, we are interested in at least 20% (45% vs. 25%) improvement in treatment efficacy for arms B versus A. For each arm, using a Simon Mini-Max two-stage design with 10% type I error rate and 10% type II error rate, 23 patients will be enrolled in the first stage of the trial. If 5 or fewer patients respond, the treatment will be stopped. If 6 or more patients show a response, 16 additional patients (a total of 39 patients per group) will be enrolled. If the total number responding is 13 or less, we will conclude that the treatment is not effective. A total sample size will be 78 patinets if both arms finish the 2nd stage. If both arms fail at the first or second stage, the trial will stop. No winner will be claimed. The sample size will be 46 if both arms fail at the first stage and 62 if only one arm fails at the first stage. If only one arm pass the second stage, the arm will be the winner. If both arms pass the second stage, we will use the posterior probability, Pr(B > A), (probability of the response rate in arm B higher than in arm A) to select the winner. A non-informative prior of beta distribution, beta(1,1) in both arms will be used to calculate the posterior probability. Arm B will be claimed as the winner if  $Pr(B > A) > \delta = 0.8$ .

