# 10.8 The Protocol Monitoring Committee (PMC)

The PMC meets once a month. The PMC reviews and evaluates safety and/or efficacy data for all physician authored clinical intervention trials. The PMC ensures the safety of patients and the validity and integrity of data. PMC reviews SAEs, deviations, Interim analysis, interim and final reports from the external Data Monitoring Committee (DMC) as well as audits both internally and externally. The PMC can make the following determinations, Accepted, Acceptable with Corrective Action and Tabled.

Investigators of studies, which are designated to be reviewed by the PMC for data and safety monitoring, shall provide an interim analysis report of the study's progress and summary of adverse events and deviations based on the phase of the study and the associated risk of the study or more often if applicable. The external DSMB (if applicable) shall forward its report for high-risk studies designated for external review at least annually or more often if applicable.

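### After the 12-patient escalation, up to 57 combination patients are treated at the chosen vorinostat dose with no quantified toxicity boundary; a prespecified review boundary would be a cheap improvement

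*Combined protocol and SAP*

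**What the plan says.** Sections 8.2.1 to 8.2.3 define the DLT, set the target at 30%, use a 21-day window and apply the mCRM to 12 patients. Section 8.2.3 leaves it to a DMC to declare the MTD once the estimates are consistent. Section 5.2 then states: "Once a MTD is determined, the phase Ib expansion and randomized phase two portions of the trial can begin accrual". Section 2.1 places the expansion "in 18 NSCLC patients who have been previously treated with anti-PD-1 or anti-PD-L1 therapy". In section 8.2.6 each phase II arm starts with 23 patients, and if it passes, "16 additional patients (a total of 39 patients per group) will be enrolled".

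After escalation, the only interim rule with a number is the Simon look in section 8.2.6: "If 5 or fewer patients respond, the treatment will be stopped". Table 14 names the winner on response alone.

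The safety provisions for these later phases are qualitative:

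- Section 5.10 lists as a ground for early termination: "Incidence or severity of adverse drug reaction in this or other studies indicates a potential health hazard to subjects".
- Section 10.8 has the PMC meet monthly and review SAEs and interim reports. How often this trial reports to it depends on phase and risk. Its outcomes are listed thus: "The PMC can make the following determinations, Accepted, Acceptable with Corrective Action and Tabled".
- Sections 10.9 and 10.10 allow suspension or termination for serious harm or unacceptable risk, with no figure attached.
- Table 7 in section 5.2.1.2 manages individual patients and does not monitor a group rate.

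**The concern.** The escalation is small and can pick a dose whose true DLT rate is well above 30%. The plan's own simulations show this. Most combination exposure comes afterwards, and there the committee reviewing safety has no benchmark to set the accumulating DLTs against. It would have to decide during the trial, without a yardstick agreed beforehand, how many events are too many. Meanwhile Arm B could be named the winner, because that rule does not look at toxicity.

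At stake are the protection of patients in phase Ib and Arm B, and the claim that the dose carried forward has a DLT rate near 30%.

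**Working it through.** **1. Exposure after escalation.** Inputs: 18 (section 2.1) and 23 + 16 = 39 (section 8.2.6). The maximum is 18 + 39 = 57 combination patients, or 57/12 = 4.75 times the escalation sample. If Arm B stops at stage 1, it is 18 + 23 = 41.

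**2. The plan's own figures.** True rates are from Table 12 and selection percentages from the mCRM rows of Table 13.

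| Scenario | True DLT rate at 100 / 200 / 400 mg | Selected above the 30% target |
|---|---|---|
| 1 | 1 / 10 / 30% | 0% |
| 2 | 30 / 40 / 60% | 36.6 + 8.9 = 45.5% |
| 3 | 10 / 30 / 50% | 25.1% |
| 4 | 5 / 10 / 30% | 0% |

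In section 8.2.4's words, "In Scenario 3 with 200mg as true MTD, the probability of 200mg as MTD is 53.2% by mCRM design". Table 13 adds 21.7% at 100 mg and 25.1% at 400 mg.

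**3. Reproduction.** All mCRM paths were enumerated exactly: four cohorts of three, start at 200 mg, no upward skipping, logistic model with intercept 3, gamma(1,1) prior, and the dose with estimated rate closest to 0.30. The plan does not say how the standardized doses are set, so this is an assumption. Setting them at the prior median and using the posterior mean DLT rate matches best. For 200/400 mg at steps 2 to 4 of the worked example it gives 10.3/25.5, 11.3/28.7 and 11.7/30.1%, against the plan's 10.3/25.5, 11.4/28.7 and 11.7/30.1%.

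| Scenario | Recomputed 100 / 200 / 400 mg | Table 13 |
|---|---|---|
| 1 | 0.4 / 16.3 / 83.3% | 0.4 / 16.3 / 83.3% |
| 2 | 55.0 / 36.2 / 8.8% | 54.5 / 36.6 / 8.9% |
| 3 | 21.4 / 53.2 / 25.4% | 21.7 / 53.2 / 25.1% |
| 4 | 1.0 / 15.7 / 83.3% | 1.0 / 15.5 / 83.5% |

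Over-target selection is 36.2 + 8.8 = 45.0% in Scenario 2 and 25.4% in Scenario 3. The five other conventions tried extend the range to 42.2–60.9% and 17.1–27.3%.

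Section 8.2.3 also says that a DLT at 200 mg leads to 100 mg. Enforcing that after the first cohort gives 29.9 + 6.7 = 36.6% in Scenario 2 and 22.2% in Scenario 3 (range over conventions 35.1–43.2% and 17.1–24.1%). Table 13 therefore matches the mCRM without that rule, and the two passages need reconciling.

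**4. Precision of the chosen dose.** The worked example in section 8.2.3 ends with 3 DLTs in 9 patients at 400 mg. The exact 95% limits are the 2.5% point of Beta(3, 7) and the 97.5% point of Beta(4, 6): 7.5% to 70.1%.

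**5. What a boundary could do (illustration).** With the plan's beta(1,1) prior, x DLTs in n patients give a Beta(1 + x, 1 + n − x) posterior. Flag when Pr(DLT rate > 0.30) > 0.95, looking after every 9 patients. At n = 9, x = 4 gives 0.850 and x = 5 gives 0.953, so the limit is 5/9. The same step gives 9/18, 12/27, 16/36, 19/45 and 22/54. An exact sequential binomial recursion over these looks, with all patients assumed evaluable, gives:

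| True DLT rate | Probability of triggering review | Mean patients |
|---|---|---|
| 10% | 0.1% | 54.0 |
| 20% | 2% | 53.0 |
| 30% | 19% | 47.5 |
| 40% | 65% | 33.9 |
| 50% | 96% | 19.8 |
| 60% | 99.9% | 12.7 |

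If Arm B stops at stage 1, the 41 patients allow looks only up to 36. The probability is then 53% at a true 40% and 88% at 50%.

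**The case against.** A reader might infer that nothing in the plan could stop an over-toxic dose, or that a known toxicity above 30% meets no stated criterion. The documents do not support this. Section 5.10 names the incidence of adverse reactions and does not exclude known ones. Section 10.10 covers unacceptable as well as unexpected risk, the PMC meets monthly, and SAEs reach the sponsor within 24 hours. What is missing is a number.

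A reader might also infer that an over-toxic dose goes forward in 25–46% of trials whenever toxicity is worse than guessed. Scenario 4 also carries that label, and there the figure is 0%, because only the back-up dose is more toxic. The range belongs to Scenarios 2 and 3. It falls to about 22–37% under the first-cohort rule, and it assumes that the DMC adopts the mCRM output. Scenario 2 is also something of a stress test: section 4.2.1 reports no DLTs at 200 mg BID given 14 days of 21, and a single-agent MTD of 400 mg daily.

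The illustrative boundary has limits too. Most of Scenario 2's 45.5% is a dose at a true 40%, where review is missed in 35% of trials. The 19% pause probability falls on the 30% rate that the plan is aiming for. Pretreated and naive patients are pooled. DLT adjudication, written for escalation, would have to be extended. Section 5.2.1.2 says of pembrolizumab-associated events: "These adverse events may occur shortly after the first dose or several months after the last dose of treatment". A cycle 1 count cannot see late ones. All of this stands and bears on how the boundary is set, but none of it supplies a benchmark where the plan has none.

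**Conclusion.** The point holds as a cheap improvement. It does not show an error in the plan. Up to 57 patients (41 if Arm B stops at stage 1) receive the combination at the chosen dose with only qualitative safety criteria and a numeric interim rule confined to response. The risk that the chosen dose exceeds the 30% target is 45.5% and 25.1% in Scenarios 2 and 3 by Table 13, about 37% and 22% with the first-cohort rule, and zero in Scenarios 1 and 4.

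This rests on three assumptions: that the mCRM recommendation is adopted, that the true rates are those of Table 12, and, for the figures with the first-cohort rule, the dose-label convention that best reproduces Table 13. At true rates of 40%, 50% and 60%, 57 patients would yield 57 × 0.40 = 22.8, 28.5 and 34.2 expected cycle 1 DLTs. These are ceilings: they assume full accrual and no action by the existing oversight.

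**What to change.** In sections 5.10 and 8.2.6, prespecify a boundary on the cumulative cycle 1 DLT rate in combination patients that triggers PMC review. Use the plan's own DLT definition, 30% target and beta(1,1) prior, and report the operating characteristics beside Table 13. State that while the PMC reviews, accrual to phase Ib and randomization to both phase II arms pause together, so that the control arm stays concurrent.

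The 0.95 cut-off, the nine-patient looks and the pooling of pretreated and naive patients are illustrations for the sponsor to settle. Any decision on dose or treatment remains with the sponsor and PMC. Say plainly that the boundary does not cover late immune events. Reconcile Table 13 with the first-cohort rule in section 8.2.3 in the same amendment.

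The cost is a paragraph, a small table, and DLT adjudication extended to phase Ib and Arm B, using the existing committee and adverse events already recorded from the first dose. In the illustrated version the downside is about a 19% chance of a review pause at exactly 30%, and 2% at a true 20%.

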## **6.0 TRIAL FLOW CHART**

## 6.1 Study Flow Chart\*

Trial Period:		Treatment Cycles								End of Treatment	Post-Treatment		
	Study					To be		ated be	eyond		Safety		Survival
Treatment Cycle/Title:	Screening (Visit 1)	1	2	3	4	5	6	7	8	Discon	Follow- up	Follow Up Visits	Follow- Up
Scheduling Window (Days):	-27 to c1d1 e		± 7	± 7	± 7	± 7	± 7	± 7	± 7	At time of Discon	30 days post last dose of study drug	Every 8 weeks post discon	Every 12 weeks
Screening Consent	Χ												
Informed Consent	Х												
Inclusion/Exclusion Criteria	Х												
Demographics and Medical History	Х												
Prior and Concomitant Medication Review	Х	Х	Х	х	Х	Х	х	Х	Х				
Vorinostat compliance review/Pill Diary		Х	Х	х	Х	Х	Х	Х	Х	Х			
Trial Treatment Administration		Х	Х	Х	Х	Х	Х	Х	Х				
Post-study anticancer therapy status										×	Х		Х
Survival Status		Х	Х	Х	Х	Х	Х	Х	Х	Х			Х
Review Adverse Events	Χ †	Х	Х	Х	Х	Х	Х	Х	Х	Х	Х		
Full Physical Examination	Х												
Directed Physical Examination		Х	Х	Х	Х	Х	Х	Х	Х	Х	Х		
Vital Signs and Weight	Х	Х	Х	Х	Х	Х	Х	Х	Х	Х	Х		
ECOG Performance Status	Х	Х	Х	Х	Х	Х	Х	Х	Х		Х		
Pregnancy Test – Urine or Serum b-HCG	Х	Х	Х	Х	Х	Х	Х	Х	Х		Х		

Trial Period:					Cycle	es				End of Treatment	Post-Treatment		
	Study					To be		ated be	eyond		Safety		Survival
Treatment Cycle/Title:	Screening (Visit 1)	1	2	3	4	5	6	7	8	Discon	Follow- up	Follow Up Visits	Follow- Up
Scheduling Window (Days):	-27 to c1d1 e		± 7	±7	± 7	±7	± 7	± 7	± 7	At time of Discon	30 days post last dose of study drug	Every 8 weeks post discon	Every 12 weeks
PT/INR and aPTT	Х	X (C1D15 -C1D21											
CBC with Differential	Х	Х	Х	Х	Х	Х	Х	Х	Х		Х		
Comprehensive Serum Chemistry Panel	Х	Х	Х	х	Х	Х	Х	Х	Х	Х	Х		
Magnesium	Х	Х	Х	Х	Х	Х	Х	Х	Х	Х	Х		
Urinalysis	Х												
T3, FT4 and TSH	Х	Х	Х	Х	Х	Х	Х	Х	Х	Х	Х		
Echocardiogram g	Х												
EKG	Х												
Tumor Imaging (CT Thorax/Abdomen)	Х			Х		Х		Х		Х		X d	
Brain MRI or Brain CT	Х												
Archival or Newly Obtained Tissue Collection a,b	Х	X (C1D15 -C1D21											
Correlative Studies Blood Collection c	X c	X c		Х		Х		Х		Х		Х	

Trial Period:		Treatment Cycles						End of Treatment	Po	st-Treatme	nt		
	Study					To be		ated be	yond		Safety		Survival
Treatment Cycle/Title:	Screening (Visit 1)		2	3	4	5	6	7	8	Discon		Follow Up Visits	Follow- Up
Scheduling Window (Days):	-27 to c1d1 e		± 7	± 7	± 7	± 7	± 7	± 7	± 7	At time of Discon	30 days post last dose of study drug	Every 8 weeks post discon	Every 12 weeks

\*All clinic visits and tests (including labs, imaging studies and biopsies) will have a plus or minus 7 day window for completion.

<sup>a All patients in the study are required to have a pre-treatment biopsy, where feasible, or archival tissue from after the most recent line of therapy, which will be tested for PD-L1 and nanostring analyses.

<sup>b C1D15-21 biopsies will be done on patients in the phase I dose escalation, phase Ib and phase II parts of the study, where feasible. PD-L1 and Nanostring studies will be completed on all of these biopsy specimens.

<sup>c Timepoints for the first two correlative study blood collection include first during Screening or on C1D1, and second on C1D15. The remainder of the blood collections will occur with the reimaging scans. Histone acetylation studies will be run on serial PBMC draws in all patients (includes phase I dose escalation, phase Ib expansion and phase II). The blood will be collected in five 10 mL green top (sodium heparin) tubes for a total of about 50mL of whole blood.

<sup>d Subjects who discontinue trial treatment for a reason other than disease progression will move into the Follow-Up Phase and should be assessed every 8 weeks (56 ± 7 days) by radiologic imaging to monitor disease status. After 1 year, the imaging time point will occur every 12 weeks (± 7 days).

<sup>e The main study screening window will occur within 28 days prior to the first study treatment. Note additionally that screening laboratory blood and urine studies must be obtained within 10 days of C1D1, with the exception of pregnancy testing in applicable patients, which must be obtained within 72 hours of first treatment.

f Only serious adverse events will be collected during the screening window.

<sup>9 Echocardiogram will be performed at screening for baseline, and may be repeated if clinically indicated per the treating investigator. Echocardiogram should be performed within 30 days of treatment initiation.

